
Primary Objectives:
 
 • To determine the safety and tolerability of three different doses of intranasal insulin in patients with Parkinson's disease (PD) 	

Secondary Objectives:
 
 • To evaluate efficacy of intranasal insulin on cognitive functioning in PD • To evaluate efficacy of intranasal insulin on motor function in PD • To evaluate efficacy of intranasal insulin on mood and apathy in PD • To identify which outcome measures are most sensitive to effects of intranasal insulin in PD 	
STUDY DESIGN	
Study Type	Dose-finding
Control Type	None
Study Indication Type	Dose-finding, safety
Blinding Schema	Double blinded
Device	SipNose nasal device
Study Design	randomized, parallel-group, double blind, placebo-controlled
Planned Duration of Subject Participation	8 weeks (Treatment duration: 3 weeks)
PRIMARY ENDPOINTS	

 • Composite safety event of either: a reduction of fasting glucose to <70 mg/dL or an unintended reduction of weight >5% • Pre-post change in safety measures (fasting glucose and weight) • Number of AEs and SAEs 	
SECONDARY ENDPOINTS	

 • Pre-post change in cognitive function measures 	

 • Pre-post change in motor function measures • Pre-post change in mood and apathy measures 	
INVESTIGATIONAL PRODUCTS, DOSE AND MODE OF ADMINISTRATION	
Investigational Product	
Regular insulin (Novolin-R) in 3 different doses and placebo
 
Dose 1, group with 7 participants: 20 IU/IN (10 units IN in one nostril twice daily x 21 days, volume 100 µl)
 
Dose 2, group with 7 participants : 40 IU/IN (10 units IN in each nostril twice daily x 21 days, volume 100 µl)
 
Dose 3, group with 9 participants: 80 IU/IN (20 units IN in each nostril twice daily x 21 days, volume 200 µl)
 
Dose 4, group with 7 participants: placebo (each nostril, twice daily)

SUBJECT SELECTION	
Targeted Accrual	30 subjects. We estimate a need to consent 50 participants in order to reach this goal.
INCLUSION CRITERIA	

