The most common side effect with intranasal insulin administration noted is transient local or nasal irritation. Please refer to Table 3 of the Schmid et al., 2018 review for a summary of the local or nasal effects of Intranasal Insulin in humans. In 2012, Craft et al reported, that number of adverse events was higher for the 20 IU and 40 IU when compared to the placebo group; however, there were no SAE's and mostly minor AEs such as rhinitis were reported (Table 4, (Craft et al., 2012)). Similar minor AEs were reported in the 2017 by Craft et al using intranasal insulin (Supplementary table 2, (Craft et al., 2017)). All the documents are attached. Overall, intranasal insulin at the proposed dose in this protocol, is expected to be safe with limited side effect profile. We plan to monitor the subjects for hypoglycemia and Insulin levels.

2 Summary of Device Description

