7.3.6 Laboratory Samples

At the screening visit, the laboratory samples will be drawn independent of fasting or non-fasting status.

At the baseline and final visit, all subjects will be required to fast for a minimum of 12 hours prior to collection of blood sampling on designated fasting visits.

At the baseline visit, the subject will receive the first intranasal dose in clinic. Once before the administration of the first dose (baseline) and twice after the administration of the first dose (approximately 15 minutes and 30 minutes after first dose), glucose finger sticks will be performed to measure blood sugar levels for patient safety.

See **Table 3** for specific list of laboratory assessments

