10.2 Subject Withdrawal

Subject may withdraw from study at any time for any reason without penalty or be terminated from the study by the clinical investigator (see provisions for termination by study team.) Investigational team will document the reason(s) for withdrawal. In the event a subject chooses to withdraw from study before Visit 3, the safety procedures described in Section 7.3 will be performed ideally within 3 days following subject's decision to withdraw. For all subjects who withdraw, all final safety assessments will be collected regardless of time elapsed since previous visit. In addition to the termination visit, subjects who withdraw early will be contacted within 7 days by study staff via telephone to assess development

of new and/or ongoing AEs and concomitant medications. Efforts will be made to recruit subjects to replace any withdrawals before randomization so as to maintain an n=30.

Subject's participation may be terminated at the discretion of the investigator. Individuals may be withdrawn for the following reasons:

- Clinically significant adverse events
- Lost to follow-up
- Protocol violations
- Inability to tolerate study medication
- Other

11 Adverse Events (AE) and Serious Adverse Events (SAE)

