12.2 Statistical Analysis of Primary Aim – safety, tolerability and adverse events

To assess safety and tolerability of the study drug at varying dose levels, AEs and SAEs will be categorized and summarized by study group. We will descriptively note if any group was more likely to have experienced a particular AE/SAE or generally experienced more AEs/SAEs throughout the course of the study; if we notice a significant ‘spike’ associated with a particular dosing group for a certain event, we’ll construct a chi-square test to see if it’s statistically significant. We will also assess the number of and reason for early withdrawals in each study group.

We will also monitor two key safety measures: 1) a fasting glucose < 70 mg/dL and 2) an unintended weight loss of >5% (relative to the patient’s weight at visit 2). The number of participants in each group who experience either or both of these events will be counted and descriptively compared. We will then compare the change in fasting glucose and weight at Visit 2 (Baseline/Initial Treatment) and Visit 3 (Final Treatment/Safety). In the event of an early withdrawal, measures taken at the early withdrawal visit will be used in place of Visit 3 data. We will descriptively note if any dosing group was more inclined to experience one or both of these safety events. In a similar fashion, if we notice a significant ‘spike’ associated with a particular dosing group, we’ll construct a chi-square test to see if it is statistically significant.

Secondarily, we will report the incidence of mild, moderate, and severe hypoglycemia overall and by group. Mild hypoglycemia will be defined as $54 \text{ mg/dL} \leq \text{fasting glucose} < 70 \text{ mg/dL}$; moderate hypoglycemia is $40 \text{ mg/dL} \leq \text{fasting glucose} < 54 \text{ mg/dL}$; and severe hypoglycemia is $\text{fasting glucose} < 40 \text{ mg/dL}$.

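### Section 12.2 grades hypoglycaemia on fasting glucose alone, so post-dose finger sticks and reported episodes have no stated place in the graded incidence

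*Combined protocol and SAP*

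**What the plan says.** **Analysis.** Section 12.2 of the combined protocol and SAP sets two safety events to be counted by group: "We will also monitor two key safety measures: 1) a fasting glucose < 70 mg/dL and 2) an unintended weight loss of >5" per cent, the weight loss being relative to Visit 2. It then adds: "Secondarily, we will report the incidence of mild, moderate, and severe hypoglycemia overall and by group". The three grades are fasting glucose from 54 to below 70 mg/dL (mild), from 40 to below 54 (moderate) and below 40 (severe). For participants who leave early, "In the event of an early withdrawal, measures taken at the early withdrawal visit will be used in place of Visit 3 data".

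**Endpoints.** The protocol summary and 4.1 define the composite on the same measure: "Composite safety event of either: a reduction of fasting glucose to <70 mg/dL or an unintended reduction of weight >5" per cent. Section 4.3 lists plasma glucose below 70 mg/dL as a safety endpoint and does not mention fasting.

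**Measurement.** Section 7.3.6 asks for one finger stick before the first clinic dose and then "twice after the administration of the first dose (approximately 15 minutes and 30 minutes after first dose), glucose finger sticks will be performed". The purpose that the section gives is "to measure blood sugar levels for patient safety". Table 3 gives finger sticks a row of their own (Visit 2 only) and fasting glucose another (Visit 2, Visit 3 and early withdrawal). After withdrawal, "the safety procedures described in Section 7.3 will be performed ideally within 3 days following" the decision to leave (10.2).

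**Reporting.** Section 7.3.3 treats any blood glucose below 70 mg/dL as clinically significant and has episodes reported to the study team. Section 7.3 turns clinically significant changes into adverse events, and 12.2 summarises those by group.

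**The concern.** The trial's main question is whether three doses of intranasal insulin are safe. Section 1.1.5 names hypoglycaemia as the most common side effect of this insulin by the subcutaneous and intravenous routes, and says of this trial: "We plan to monitor the subjects for hypoglycemia and Insulin levels". The graded incidence is the only output in the plan that sorts hypoglycaemia by glucose level across the dose groups.

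As worded, that output rests on a fasting sample for which the readable text gives no time since the last dose. The only scheduled readings with a stated time after a dose are the two finger sticks, and Section 12 mentions neither them nor the reported episodes. A participant with a recorded low soon after dosing can therefore appear as having no hypoglycaemia of any grade, while the adverse-event summary shows an event. A reader of the graded result would not know which measurements stand behind a zero.

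**Working it through.** The plan states no figure on this point, so the check compares the sections and then counts readings.

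**1. Which scheduled readings after the first dose meet the 12.2 definition?**

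| Reading | Source | Called fasting glucose? | Enters the grades as worded? |
|---|---|---|---|
| Finger stick, about 15 min after first dose | 7.3.6, Table 3 | No, separate row | Not stated; natural reading is no |
| Finger stick, about 30 min after first dose | 7.3.6, Table 3 | No, separate row | Not stated; natural reading is no |
| Visit 3 or early-withdrawal glucose | Table 3, 12.2 | Yes | Yes |
| Reported episode, with or without a value (unscheduled) | 7.3.3 | No | Not stated |

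The Visit 2 fasting sample is left out because 12.2 uses it as baseline. The glucose in the Visit 3 metabolic panel is treated as the same time point as the Visit 3 fasting glucose.

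**2. Count.**
- Participants: 7 + 7 + 9 + 7 = 30, which matches the planned total; on insulin, 7 + 7 + 9 = 23.
- Scheduled time points after the first dose, per completer: 2 + 1 = 3, of which 1 is graded and 2 are not (2/3 = 67%).
- Whole trial: 30 × 2 = 60 of 30 × 3 = 90 time points outside the grades. Insulin arms: 23 × 2 = 46 of 23 × 3 = 69.

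**3. What the count does not show.**
- Scheduled doses: 21 days × 2 = 42. The finger sticks follow only the first, 1/42 = 2.4%. With the ±5 day window for Visit 3 the doses range from 16 × 2 = 32 to 26 × 2 = 52.
- The readable text schedules no glucose measurement at home. The 67% is thus a share of readings, not of events, and no rate of lows is given from which an under-count could be computed.
- One participant moved into or out of the count shifts an arm by 1/7 = 14.3 or 1/9 = 11.1 percentage points. That holds for any yes/no outcome in arms of this size and is given only for scale.

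**4. Follow one participant through the plan.** Suppose the 30-minute stick lies from 54 to below 70 mg/dL and the Visit 3 fasting value is 70 or above.
- Adverse-event summary: one event, through 7.3.3 and 7.3.
- Graded incidence, natural reading: none.
- Graded incidence, if sticks at a fasting visit count as fasting: one mild event.

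The same data thus give two different graded results, and one of them disagrees with the adverse-event summary.

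**The case against.** **The grades may be meant only to split the composite's glucose component.** They divide the range below 70 mg/dL exactly, they are introduced as secondary, and the composite is fasting-only in the summary, 4.1 and 12.2. A fasting value at one scheduled visit is also collected alike in every arm. This is a fair reading and a good reason to keep that split. It does not explain why an output named as the incidence of hypoglycaemia should stop there, and the plan gives no reason.

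**Post-dose lows are reported elsewhere.** This stands. Sections 7.3 and 7.3.3 should make them adverse events, 12.2 summarises those by group, and their number is a primary endpoint. A reader might infer that such lows are lost to safety reporting; the documents do not support that. What is missing is grading by glucose level: 4.3 asks for adverse-event severity, but no section ties it to glucose.

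**The finger sticks may count already.** Visit 2 is a fasting visit with a fast of at least 12 hours before blood sampling, so an analyst could treat them as fasting values. Table 3's separate rows point the other way without settling it. To say that the plan firmly excludes them would therefore be too strong.

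**Section 4.3 is weak support.** It speaks of plasma glucose, which does not clearly include finger sticks. The broader wording in 7.3.3 carries more weight.

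**No consequence is shown.** This is true in numbers: the analysis is descriptive, 7.3.3 expects few lows, and no under-count can be calculated.

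**Conclusion.** The point holds in a limited form. On the natural reading, the graded incidence uses one post-treatment value per participant and leaves out two scheduled post-dose readings and any reported episode. It can then under-count and disagree with the adverse-event summary. The size of any under-count cannot be derived.

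Two stronger inferences are not supported. One is that two thirds of hypoglycaemic events would be missed: the two-thirds figure counts scheduled readings, and the sticks cover one dose of 42. The other is that the fasting-glucose composite is wrong: it is defined consistently and may be deliberate.

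The conclusion assumes that Table 3's separate rows mean separate measures and that the Visit 2 fasting sample is baseline. Sections 5.2 and 5.3 are redacted, so statements about dose timing and home measurement cover the readable text only. Severity is between minor and should-fix, with moderate confidence.

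**What to change.** Change 12.2 only.

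- Keep the fasting-glucose composite and its fasting-only severity split as defined.
- Also report the graded incidence, overall and by group, on each participant's lowest glucose recorded after the first dose, with the existing cut-offs. Sources are those already collected: the post-dose finger sticks, the Visit 3 or early-withdrawal glucose, and any reported value.
- Count each participant once, and label the source and fasting status of the value used.
- List reported episodes without a glucose value separately by group, ungraded.
- State whether the Visit 2 post-dose sticks count as fasting glucose in the fasting-only results.

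Two further clarifications are optional: a supplementary composite count using any post-dose glucose below 70 mg/dL, and a sentence that pre-dose Visit 2 lows are not events, which the wording of 4.1 already implies.

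**Cost.** Some wording, one further graded summary and a short listing; no new sample, visit or endpoint. Finger-stick and laboratory values are mixed, cut-offs written for fasting glucose are applied to values that may not be fasting, unscheduled values depend on who measures or reports, and counts may rise. The labels let a reader judge this. The wording should be settled before study staff are unblinded, which 13.6 places after database lock.

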12.3 Statistical Analysis of Second Aim – efficacy measures

For each of the efficacy outcome measures, we will report mean differences and 95% confidence intervals between Visit 2 (Baseline/Initial Treatment) and Visit 3 (Final Treatment/Safety) for each study group. In the event of an early withdrawal, measures taken at the early withdrawal visit will be used in

place of Visit 3 data, if possible. Possible trends in cognitive function, motor function, and mood and apathy scores will be addressed.

We will look at the individual components and domains assessed by the chosen cognitive, motor, mood, and apathy measures to determine if any appear to be more sensitive to IN insulin. We will also explore the data for components that have a larger dose response. That is, they increase or decrease as the dose-level increases.

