4.2 Secondary Endpoints

- Pre-post change in cognitive function
- Pre-post change in motor function

- Pre-post change in mood and apathy

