7.5.5 Learning and Memory

7.5.5.1 *Logical Memory*

Logical Memory is an auditory story-recall subtest from the Wechsler Memory Scale – Fourth Edition (Wechsler, 2009). Participants are read two short stories and are immediately asked to recall as much detail as they can remember. Following a 20-30 minute delay, they are asked again to recall details from the stories. Finally a forced-choice Yes/No recognition task will also be administered.

7.5.5.2 *Hopkins Verbal Learning Test- Revised*

The Hopkins Verbal Learning Test- Revised is a list-learning task which includes a list of 12 words (Brandt, 1991). There are 3 semantic categories within each list, meaning 4 of the words are semantically related. Standard test administration includes 3 learning trials where the entire list of 12 words is verbally presented to the participant and they are asked to repeat as many words as they can recall after each presentation. The test also includes a 20-25 minute delay where participants are then asked to recall the words previously learned. This is followed by a 24-word yes/no recognition task, which includes the 12 target words from the original list and 12 foils. Alternate forms will be used at different time points in the study to reduce the potential for practice effects.

7.5.5.3 *Brief Visuospatial Memory Test - Revised*

The Brief Visuospatial Memory Test- Revised is a visuospatial learning and memory task which includes 6 shapes displayed in an array (Benedict, 1997). Standard administration includes 3 learning trials where the participant is allowed to view the page with the 6 figures for 10 seconds and then they are asked to draw the shapes as accurately as they can in the correct location on the page. The test also includes a 20-25 minute delay where participants are then asked to recall the figures previously learned. This is followed by a 12 item yes-no recognition task, which includes the 6 figures they were initially exposed to and 6 foils. Alternate forms will be used at different time points in the study to reduce the potential for practice effects.

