12.1 Statistical Analysis Overview

Due to the small sample size of this study, statistical analysis will be mainly exploratory and descriptive: t-tests (or Mann-Whitney u-tests if normality of the data is not met) are used to compare the difference of a continuous measure between groups (such as patient age at baseline, various efficacy measures), and contingency tables and chi-square tests are used to compare the difference of a categorical variable (such as patient gender at baseline, various safety and adverse events).

To minimize the potential confounding effects of gender and MOCA score on the treatment effect, we will use stratified block randomization when assigning patient to one of the four study groups. The stratification factors will be gender (male/female) and MOCA score (low <22/30 and high>23/30). We will use block size of four.

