12.4 Statistical Power

As stated above, due to the sample size limitation of this study, no particular statistical power is under consideration during the study design phase with the intent to detect a meaningful clinically significant difference between study groups for any of the primary or secondary outcome measures; statistical analysis of this study will be mainly exploratory and descriptive.

The overall goal of the study is to identify a safe dose intranasal insulin with trends towards the secondary outcomes. Three different doses (and placebo) will be used, with the highest number of subjects (9) in the group with the highest dose, a model previously used by Finger et al. (2014).

13 Study Conduct Considerations

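### Section 12.3 gives intervals only for change within each arm and does not base its statements about insulin effects on the placebo comparison

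*Combined protocol and SAP*

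**What the plan says.** The Protocol Summary describes the design as "randomized, parallel-group, double blind, placebo-controlled", with arms of 7 (20 IU), 7 (40 IU), 9 (80 IU) and 7 (placebo). Section 4.2 defines the secondary endpoints as changes over time, for example "Pre-post change in cognitive function". Section 3.2 includes, as a secondary objective, finding the outcome measures that respond most to insulin. Section 12.4 states: "The overall goal of the study is to identify a safe dose intranasal insulin with trends towards the secondary outcomes".

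For the efficacy analysis, section 12.3 says "we will report mean differences and 95% confidence intervals between Visit 2 (Baseline/Initial Treatment) and Visit 3 (Final Treatment/Safety) for each study group". It adds that possible trends will be addressed and that components and domains will be examined "to determine if any appear to be more sensitive to IN insulin". It also looks for a dose response, meaning that "they increase or decrease as the dose-level increases". Section 12.3 does not mention placebo, a difference between arms, or a test.

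Section 12.1, the overview, says "t-tests (or Mann-Whitney u-tests if normality of the data is not met) are used to compare the difference of a continuous measure between groups", and gives efficacy measures as one example. It does not say which of the four arms are compared, whether the score is the change or the Visit 3 value, or whether an interval is given.

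For two memory tests (HVLT-R and BVMT-R), section 7.5.5 says "Alternate forms will be used at different time points in the study to reduce the potential for practice effects". No such statement is made for the other tests.

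**The concern.** A change within one arm contains any drug effect, any gain from taking the same test again three weeks later, and any placebo response. Only the comparison with the randomised placebo arm separates the first from the other two. The trial has that arm, but 12.3 does not tie its conclusions to it.

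If trends are read from within-arm changes, the tests with the largest practice gain can look the most sensitive to insulin. That would mislead on a stated secondary objective and on the overall goal in 12.4, and could steer the choice of dose and outcome measures for a later trial. Printing the placebo interval in the same table does not settle the matter, because one interval excluding zero while another includes it is not a test of the difference between them.

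The dose-response search is less exposed. A gain shared by all arms creates no gradient in expectation. Even so, 12.3 does not say whether placebo counts as dose zero.

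**Working it through.** **Inputs from the documents.** Arm sizes are 7, 7, 9 and 7 (Table 2), and 7 + 7 + 9 + 7 = 30 matches the target accrual. The interval level is 95% (12.3). No power, SD, effect size or retest gain is given for any efficacy measure, so there is no power figure to reproduce.

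**Tests exposed to practice.** Table 3 schedules nine cognitive tests at both Visit 2 and Visit 3. Two have alternate forms stated. That leaves 9 − 2 = 7: Digit Span, Trailmaking, Line Orientation, Logical Memory, Stroop, Letter Fluency and Category Fluency.

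**Assumptions.** (a) No drug effect. (b) Every arm gains d SD of the change score, with d = 0, 0.3 or 0.5. (c) Changes are normal, with higher meaning better. (d) A within-arm 95% CI wholly above zero is read as improvement, a rule the plan does not state.

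**Chance that one arm improves.** p(n, d) = P(T > t₀.₉₇₅,ₙ₋₁), where T is noncentral t with n − 1 df and noncentrality d√n.

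**At least one of the three insulin arms improves:** A = 1 − (1 − p₇)²(1 − p₉). **The same while placebo does not:** A × (1 − p₇).

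| Shared gain d | p₇ | p₉ | A | A and placebo does not improve | Expected tests flagged, 7 × A |
|---|---|---|---|---|---|
| 0 | 0.025 | 0.025 | 0.073 | 0.071 | 0.5 |
| 0.3 | 0.099 | 0.122 | 0.288 | 0.259 | 2.0 |
| 0.5 | 0.200 | 0.262 | 0.528 | 0.422 | 3.7 |

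At d = 0.3, for example, A = 1 − (1 − 0.099)²(1 − 0.122) = 0.288, and 0.288 × (1 − 0.099) = 0.259. The last column also assumes the same gain on all seven tests.

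**With a placebo contrast.** I simulated 40,000 trials per setting, with gains of 0, 0.3 and 0.5 and baseline-to-final correlations of 0.4, 0.6 and 0.8. The chance that any of the three insulin-minus-placebo intervals lies above zero was:

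- two-group t-test on change: 0.059–0.065
- two-group t-test on final score: 0.060–0.064
- pooled four-arm change: 0.058–0.061
- four-arm ANCOVA (25 df): 0.058–0.062

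The rate does not depend on the gain. Over seven tests, 7 × 0.06 = 0.4 are expected to be flagged.

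**Precision.** In SD of change, the standard error is 1/√7 = 0.38 within an arm of 7 and √(2/7) = 0.53 for a 7 v 7 difference. Mean 7 v 7 half-widths, in SD of the score, are:

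| Baseline–final correlation | Pooled change | ANCOVA | Reduction |
|---|---|---|---|
| 0.4 | 1.193 | 1.019 | 1 − 1.019/1.193 = 15% |
| 0.6 | 0.973 | 0.890 | 1 − 0.890/0.973 = 9% |
| 0.8 | 0.688 | 0.667 | 1 − 0.667/0.688 = 3% |

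**What remains.** I took 13 measures with one score each: nine cognitive tests, MoCA, UPDRS III, BDI-II and Apathy Scale. With no drug effect, at least one ANCOVA contrast lies above zero in 55–56% of trials if the measures are uncorrelated, 43–45% at a between-measure correlation of 0.3, and 35–36% at 0.5. The expected number of false leads is about 0.8 (13 × 0.06) at every gain.

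**The case against.** The strongest reply is that a between-group comparison is already planned. Section 12.1 names efficacy measures among the variables for two-sample tests, and an overview need not be repeated in 12.3. Such a test of each dose against placebo, on change or final score, would hold the rate near 6%. This stands in part: it would be wrong to say that no between-group comparison is planned. But four arms give six pairs, only three of them against placebo, and 12.1 does not commit to those three, to a score, or to an interval.

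Second, the 29% and 53% depend on an unstated reading rule and an assumed gain. That also stands. Under a much stricter informal rule, an insulin interval lying wholly above the placebo interval, simulation gives about 0.8% at gains of 0, 0.3 and 0.5 SD. The result therefore depends on how the table is read, which is the reason to specify the contrast.

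Third, the placebo interval is reported, so a reader could derive the differences. This is true of mean changes, but it leaves the main estimate to the reader and does not govern the plan's own trend and sensitivity statements.

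Fourth, the simplest repair is a placebo contrast on change; ANCOVA adds only precision. That is correct, and the choice of model is secondary to the choice of contrast.

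Finally, the analysis is openly exploratory and unpowered. That excuses wide intervals and the absence of multiplicity control. It does not justify attributing a shared gain to the drug.

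**Conclusion.** The concern holds. The only interval in 12.3 is within-arm, its trend and sensitivity statements have no comparator, and the tests in 12.1 are too loosely specified to supply one. Under the assumed rule and shared gains of 0.3 to 0.5 SD, a null drug would appear to improve a given test in at least one insulin arm in 29% to 53% of trials, and in 26% to 42% while placebo does not. A placebo contrast brings this to about 6% whatever the gain. These figures illustrate the mechanism and do not predict this trial, since no document gives a retest effect.

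The change should be made, but its weight is limited. The endpoints are secondary, there is no success rule, and the primary safety aim is unaffected.

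**What to change.** In 12.3, for each efficacy measure, report each insulin-minus-placebo difference with its 95% CI from one four-arm ANCOVA of the Visit 3 value on group and baseline value, labelled exploratory. For the MoCA, use Visit 1 as baseline, because Table 3 has no Visit 2 MoCA and the Visit 2 to Visit 3 change cannot be computed for it.

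Base the trend, sensitivity and dose-response statements on these differences, with placebo as dose zero. Keep the within-arm changes as description. Align 12.1 with the same contrasts, including any rank-test fallback. State that no multiplicity control is applied across the measures.

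The cost is SAP wording and one standard model, with no new data. The price is precision: a placebo difference is noisier than a within-arm change (standard error 0.53 v 0.38 SD of change for arms of 7), and the 7 v 7 ANCOVA half-width is about 0.7 to 1.0 SD of the score. With about 13 measures some false leads will remain, and the report should say so.
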